8. RESEARCH QUESTION AND OBJECTIVES

This study has been designed in order to describe the current non-vitamin K antagonist oral anticoagulants (NOACs) management in elderly patients in Spain.

Primary objective: To describe the pattern of usage of NOACs prescribed according to their Summary of Product Characteristics (SmPC), by current NOAC type and dose, in elderly patients (≥ 75 years-old) with non-valvular atrial fibrillation (NVAF) at the time of the study visit.

Secondary objectives:

1. To describe patients characteristics at the time of the study visit by current NOAC type stratified by duration since first NOAC initiation.
2. To describe OAC treatment management since first NOAC initiation until the study visit by duration since first NOAC initiation: previous vitamin K antagonists (VKA) treatment, first NOAC treatment duration, dose changes, switch between NOACs and reasons for switch, total NOAC treatment duration and additional antiplatelet treatment.
3. To describe the Clinical Frailty Scale grading, CFS ([19](#)), at the time of the study visit, by current NOAC type.
4. To describe first NOAC usage by NOAC type, for primary prevention or secondary prevention, at the time of first NOAC initiation.

9. RESEARCH METHODS

9.1 STUDY DESIGN

This is an observational, multicenter and cross-sectional study in NVAF elderly patients currently on NOAC treatment for their stroke prevention.

AF is classified as non-valvular AF in the absence of mitral stenosis or cardiac valvular prosthesis, since NOACs are not recommended for patients with mechanical heart valve (level of evidence B) or moderate to severe mitral stenosis (level of evidence C) ([22](#)).

The study will be conducted in approximately 50 sites in Spain. Investigators from different specialties are planned to be included as follows: 35 cardiologists, 10 hematologists and 5 geriatricians.

The design of the study impose a single visit to be performed for the informed consent signature and data collection that will coincide with one of those performed by the patients as part of routine follow-up of their disease, without interfering with usual clinical practice of the investigator.

A specific therapeutic strategy has already been assigned to each included patient, based on routine practice and without interference with the physician's prescription habits. The observational nature of the study is ensured as no diagnostic or therapeutic intervention outside of routine clinical practice will be applied.

9.2 SETTING

Approximately 500 elderly patients with NVAF currently on NOAC treatment are planned to be included in the study. To minimize selection bias at the patient level, consecutive patients from each site who meet entry criteria will be enrolled. It is planned to have a 9-month recruitment period from first site initiated, or until the sample size is achieved.

The number of patients per site to be included in the study will be initially set up to a maximum of 10 patients per site. Once the 50% of the participating sites have been initiated, the recruitment will become competitive until the end of the study and the limitation of 10 patients per site will be removed to allow sites to continue with the recruitment.

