9.2.1 Study sites

Cardiology, hematology, geriatric services at a hospital setting, specialty medical offices and nursing homes, who regularly prescribe NOACs for stroke prevention in NVAF patients may be invited to participate.

It is necessary to ensure that study population is representative of the entire national territory. Therefore, patients may be recruited from sites with different level of medical care (e.g, primary hospital, secondary hospital, private care) in several geographical areas according to

the distribution of the overall population in this area. Site selection will be performed in order to secure representativeness of the NVAF population treated with NOAC.

As a pre-study activity, sites will need to answer a site feasibility questionnaire in order to determine that the site has adequate facilities and investigator is qualified and meets the needs of the study, recruitment targets, quality and timelines in compliance with the applicable regulatory requirements.

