9.5 STUDY SIZE

It is planned that a total of approximately 500 patients will be recruited for the study. Based on such a sample size estimate, categorical variables of binomial proportions (e.g. sex) will be estimated with the precision (i.e. width of descriptive 95% confidence interval) described in the following Table 4. Calculations of the confidence intervals (CI) are based on the Clopper-Pearson method:

Table 4 Width of 95% confidence interval by prevalence of attribute:

Prevalence of attribute	Sample size
	500
10% Expected n	50
95% CI width	5.46%
20% Expected n	100
95% CI width	7.20%
30% Expected n	150
95% CI width	8.22%
40% Expected n	200
95% CI width	8.76%
50% Expected n	250
95% CI width	8.94%

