4. STUDY DESIGN

4.1 General Description

This is an observational, multicenter and cross-sectional study in NVAF elderly patients currently on NOAC treatment for their stroke prevention.

AF is classified as non-valvular AF in the absence of mitral stenosis or cardiac valvular prosthesis, since NOACs are not recommended for patients with mechanical heart valve (level of evidence B) or moderate to severe mitral stenosis (level of evidence C) (3).

The study will be conducted in approximately 50 sites in Spain. Investigators from different specialties are planned to be included as follows: 35 cardiologists, 10 hematologists and 5 geriatricians.

Document:	H:\HOR-Europe\2019\2512352 - Study on anticoagulation management - BI\Proyecto\Estadística\SAP\SAP_REBELD_version1.0_08072020.docx		
Author:		Version Number:	Version 1.0
		Version Date:	[08072020]

Template No.: RWI_TP_BIOS0013 Revision 1

Reference: RWI_WI_BIOS0015

Effective Date: 15Jun2018

The design of the study imposes a single visit to be performed for the informed consent signature and data collection that will coincide with one of those performed by the patients as part of routine follow-up of their disease, without interfering with usual clinical practice of the investigator.

A specific therapeutic strategy has already been assigned to each included patient, based on routine practice and without interference with the physician's prescription habits. The observational nature of the study is ensured as no diagnostic or therapeutic intervention outside of routine clinical practice will be applied.

Cardiology, hematology, geriatric services at a hospital setting, specialty medical offices and nursing homes, who regularly prescribe NOACs for stroke prevention in NVAF patients may be invited to participate.

The number of patients per site to be included in the study will be initially set up to a maximum of 10 patients per site. Once the 50% of the participating sites have been initiated, the recruitment will become competitive until the end of the study and the limitation of 10 patients per site will be removed to allow sites to continue with the recruitment.

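### The planned 95% CI widths treat 500 patients as independent, although patients are clustered in about 50 sites and the limit per site is lifted during recruitment

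*Protocol*

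**What the plan says.** **Precision.** Protocol 9.5 states: "It is planned that a total of approximately 500 patients will be recruited for the study". It measures precision by the "width of descriptive 95% confidence interval" and adds: "Calculations of the confidence intervals (CI) are based on the Clopper-Pearson method". Table 4 gives 5.46, 7.20, 8.22, 8.76 and 8.94% for prevalences of 10 to 50%. SAP 4.2 repeats the table. Neither document mentions a design effect, an ICC or site.

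**Sites.** Protocol 9.1 states: "The study will be conducted in approximately 50 sites in Spain". The investigators are planned as "35 cardiologists, 10 hematologists and 5 geriatricians". Under Protocol 9.2, sites enrol consecutive eligible patients, at first up to 10 each. When initiation has reached half the sites, "the recruitment will become competitive until the end of the study and the limitation of 10 patients per site will be removed". SAP 4.1 repeats the rule. No later limit per site, specialty or region is given.

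**Representativeness.** Protocol 9.2.1 says: "It is necessary to ensure that study population is representative of the entire national territory". The means it offers is the selection of sites.

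**Analysis.** The primary result is the percentage of patients by NOAC type and dose (Protocol 9.7.1, SAP 14.1.1). The protocol abstract promises 95% confidence intervals where appropriate. SAP 8 lists the summary statistics without intervals. SAP 8.2 has confidence intervals in its title but says only that no test will be done. The primary mock tables (SAP Tables 27 to 35) have no place for an interval.

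**The concern.** A binomial interval on 500 patients is correct only if patients are independent. Here they come in groups that share a clinic and often a prescriber, and the outcome is what that prescriber chose. Protocol 9.1 itself refers to physicians' prescribing habits. Patients at one site are therefore likely to resemble each other in NOAC type and dose more than patients from different sites do. The 500 then carry less information than the table implies.

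The recruitment rule affects how much less. With a limit of 10, clusters are small and of similar size. Without it, fast sites may supply many patients and slow ones few, and the loss grows with the size and inequality of the clusters. Site selection decides which sites take part, not how many patients each contributes.

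At stake is how firmly the pooled percentages can be read as Spanish practice. A reader who relies on the tabulated widths would credit the study with more precision than its design gives. If a few sites dominate, a reader could not see it from the tables available for review.

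**Working it through.** **Inputs from the documents:** N = 500 and the Clopper-Pearson method (Protocol 9.5); about 50 sites (Protocol 9.1); limit of 10, removed when about 25 sites are initiated (Protocol 9.2). **Assumed:** ICC of 0.02, 0.05 and 0.10, and the distribution of patients over sites.

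**Step 1. Reproduce the plan's figures.** Exact limits for x of 500, taking the difference of the rounded limits:

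| Prevalence | x | Limits (%) | Width (%) | Protocol Table 4 |
|---|---|---|---|---|
| 10% | 50 | 7.51 to 12.97 | 5.46 | 5.46 |
| 20% | 100 | 16.58 to 23.78 | 7.20 | 7.20 |
| 30% | 150 | 26.01 to 34.23 | 8.22 | 8.22 |
| 40% | 200 | 35.68 to 44.44 | 8.76 | 8.76 |
| 50% | 250 | 45.53 to 54.47 | 8.94 | 8.94 |

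All five rows match. Wald and Wilson intervals do not (8.77 and 8.73 at 50%). The table therefore uses the full 500, that is, a design effect of 1. SAP Table 1 differs in one row: it shows 8.76 at 50%, which repeats its 40% row; the Clopper-Pearson value is 8.94.

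**Step 2. Design effect.** DEFF = 1 + (m_w − 1) × ICC, where m_w = Σm²/Σm is the patient-weighted mean cluster size. Effective n = 500/DEFF, and the Clopper-Pearson width is recomputed at that n.

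- 50 sites of 10: m_w = 10, DEFF = 1 + 9 × ICC.
- 25 sites of 20: m_w = 20, DEFF = 1 + 19 × ICC.
- 10 sites of 30 and 40 sites of 5: m_w = (10 × 900 + 40 × 25)/500 = 20, so the result is the same as for 25 sites of 20.
- 5 sites of 60, the other 45 sharing 200: m_w = 37.78.

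**Step 3. Results at 50% prevalence (tabulated width 8.94%).**

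| Distribution | ICC | DEFF | Effective n | Width (%) |
|---|---|---|---|---|
| 50 × 10 | 0.02 | 1.18 | 424 | 9.7 |
| 50 × 10 | 0.05 | 1.45 | 345 | 10.8 |
| 50 × 10 | 0.10 | 1.90 | 263 | 12.4 |
| 25 × 20 | 0.02 | 1.38 | 362 | 10.5 |
| 25 × 20 | 0.05 | 1.95 | 256 | 12.6 |
| 25 × 20 | 0.10 | 2.90 | 172 | 15.4 |
| 5 sites supply 60% | 0.02 | 1.74 | 288 | 11.8 |
| 5 sites supply 60% | 0.05 | 2.84 | 176 | 15.2 |
| 5 sites supply 60% | 0.10 | 4.68 | 107 | 19.7 |

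At 10% prevalence (tabulated 5.46%), the widths for the same ICCs are 5.95 / 6.62 / 7.62% for 50 × 10 and 6.45 / 7.73 / 9.52% for 25 × 20.

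**The case against.** The strongest reply is that the study is descriptive and tests no hypothesis, and that Table 4 is only a planning aid. It offers sex as its example, not NOAC choice. The ICC is not in the documents, and at 0.02 with 10 patients per site the width moves only from 8.94% to 9.7%. Site selection, feasibility screening and consecutive enrolment give some protection. The visible SAP specifies no intervals for the primary outcome, so it does not yet report any that are too narrow.

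Most of this stands, and it limits the point to the planning tables and to whatever intervals are eventually reported. It does not remove the point. The direction is the same for every positive ICC, and the protocol abstract does promise intervals. The 25 × 20 result also does not need half the sites to enrol nobody: 10 sites of 30 and 40 of 5 give the same design effect.

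Stronger readings are tempting but not supported:

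- *Lifting the limit causes the problem.* Clustering is ignored at 50 × 10 as well; lifting the limit can only enlarge the effect.
- *A planned patient mix of 350/100/50 is being broken.* The 35/10/5 split counts investigators, and 10 per site is a maximum, not a quota. Nor do the documents show that equal numbers per site represent Spain better than numbers that follow site volume.
- *Geriatric sites could fall below the 50-patient minimum.* In SAP 8.5, 14.1.1, 14.3.1 and 14.3.2 that minimum covers sex, age, comorbidity, duration and the standardized differences. Specialty is not among them.
- *A ceiling of 20 per site would solve it.* 25 × 20 = 500 is one of the unfavourable cases above, and all 25 sites could be among the 35 cardiology sites. The SAP version date (08072020) is also later than the planned end of data collection, 27 April 2020.
- *No output shows site or specialty.* SAP 14.4, 14.5 and Table 44 are not visible, so this can be said only of what is.

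**Conclusion.** The concern holds in a limited form. The tabulated widths are correct for 500 independent patients and too narrow for patients clustered by site whenever the ICC is above zero. A positive ICC is plausible because NOAC type and dose depend on the prescriber. Under assumed ICCs of 0.02 to 0.10, the width at 50% prevalence is about 1.09 to 1.38 times the independent one with 50 sites of 10, and about 1.17 to 1.70 times with a weighted mean cluster size of 20.

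Only the direction is certain; the size depends on an ICC and a site distribution that the documents do not give. Dominance by a few sites is permitted, not shown. The study remains valid as a description; its stated precision needs qualifying, and its site distribution should be made visible.

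**What to change.** 1. In SAP 8.2 and 14.1.1, state that 95% CIs will be given for the primary percentages by NOAC type and dose, and compute them with site as the cluster. One way is SAS PROC SURVEYFREQ with a CLUSTER statement and Clopper-Pearson limits on the effective sample size. This requires no hypothesis test or regression model.
2. In Protocol 9.5 and SAP 4.2, say that the tabulated widths assume independent patients, and add widths for a range of ICCs such as 0.02 to 0.10. Correct the 50% row of SAP Table 1 at the same time.
3. Report the number of patients per site, and the primary outcome by investigator specialty, descriptively. Specialty is known from the site, so no new data are needed.
4. Add concentration of patients in few sites to the limitations in Protocol 9.9.

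The cost is interval columns that the visible tables lack, intervals somewhat wider than the planning table suggests, and one or two extra tables. No patients are added and recruitment is unchanged.

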9.2.1 Study sites

Cardiology, hematology, geriatric services at a hospital setting, specialty medical offices and nursing homes, who regularly prescribe NOACs for stroke prevention in NVAF patients may be invited to participate.

It is necessary to ensure that study population is representative of the entire national territory. Therefore, patients may be recruited from sites with different level of medical care (e.g, primary hospital, secondary hospital, private care) in several geographical areas according to

the distribution of the overall population in this area. Site selection will be performed in order to secure representativeness of the NVAF population treated with NOAC.

As a pre-study activity, sites will need to answer a site feasibility questionnaire in order to determine that the site has adequate facilities and investigator is qualified and meets the needs of the study, recruitment targets, quality and timelines in compliance with the applicable regulatory requirements.

9.2.2 Study population

To be eligible to participate in the study, patients must meet the following selection criteria. The patient will be considered included when he/she agrees to participate in the study by signing the informed consent.

Patients will be included in the study if all of the following criteria are met:

1. Patients are willing and provide written informed consent prior to participate in this study
2. Patients \geq 75 years-old at the time of the study visit.
3. Patients with a diagnosis of non-valvular atrial fibrillation (NVAF).
4. Patients who are being treated with NOAC treatment according to the indication approved in the SmPC.
5. Patients who have started the NOAC treatment at least 3 months prior to the study visit.

Patients will be excluded from participating in this study if the following criterion is met:

1. Current participation in any clinical trial of a drug or device.
2. Patients who have any contraindication for NOAC treatment, according to the SmPC.

A log of all patients included into the study (i.e. having given informed consent) will be maintained in the investigator site file at the study site.

9.2.3 Study visits

Patients will be invited to participate in this study during a routine medical visit for any purpose with their physician. Investigator will provide to patients the “patient information and informed consent form” and will explain the study to the patient. If patients agree to participate, after signing the informed consent, investigator will assess the Clinical Frailty Scale (19), the Modified EHRA scale for AF related symptoms (23), the NYHA classification of heart failure (24) (refer to Annex 3) and the CHA2DS2-VASc and HAS-BLED scales, and include the scores directly in eCRF after evaluating the patient’s functional status and patient’s medical records. The investigator will review the medical records in order to complete other variables needed to address study objectives that will mainly be obtained

directly from patient medical records or requested to the patient at the study visit if not available in medical records (refer to [Section 9.4](#)). The end of the single study visit is the end of the study for each patient.

9.2.4 Study discontinuation

Boehringer Ingelheim reserves the right to discontinue the study overall or at a particular study site at any time for the following reasons:

1. Failure to meet expected enrolment goals overall or at a particular study site
2. Administrative reasons (i.e. study rejected by the hospital director)
3. Violation of GxP (as applicable), the study protocol, or the contract by a study site or investigator, disturbing the appropriate conduct of the study

The investigator / the study site will be reimbursed for reasonable expenses incurred in case of study termination (except in case of the third reason).

9.3 VARIABLES

9.3.1 Exposures

Patients in this study will be currently on treatment with NOAC for their NVAf, according to the indication approved in their SmPC, and initiated it at least 3 months before the study visit. Prescription of the treatments will have been done under the sole responsibility of the healthcare professional and before considering the participation in the study.

As this is an observational study, designed to reflect as faithfully as possible real-life clinical practice, the decision to start treatment with NOAC is prior to and independent of the participation of the patient in the study and based on medical judgment criteria and routine clinical practice. In addition, no intervention, either diagnostic or therapeutic, will be applied to patients other than that used for routine clinical practice.

9.3.2 Outcomes

9.3.2.1 Primary outcome

The primary outcome is the pattern of usage of non-vitamin K oral anticoagulants (NOACs) prescribed according to their Summary of Product Characteristics (SmPC), based on the percentage of patients by NOAC type and dose the patient is taking at the time of the study visit. Timeframe to complete data collection for this outcome is one day, the study visit day.

Table 2 Primary variable collected at the time of the study visit

[figure not shown]
Variable	Obtained from medical records
Current NOAC active substance and dose	x

9.3.2.2 Secondary outcomes

Secondary outcomes are:

1. Patient's characteristics at the time of the study visit by the NOAC type that the patient is taking at the time of the study visit. Patients will be also stratified by the duration since the first NOAC initiation date until the study visit date (> 4 months / ≤ 4 months). (see Related patient's characteristics covariates: refer to [Section 9.3.3](#), [Table 3](#)).
2. OAC treatment management (since first NOAC initiation until the study visit date), based on the following variables:
 - Previous vitamin K antagonist (VKA) treatment (yes/no), VKA treatment duration in years, reason for switch to NOAC,
 - Duration since NVAf diagnosis until first NOAC initiation,
 - Duration of first NOAC treatment (first NOAC active substance, start and stop date, first NOAC dose and its dose changes),
 - Switch to new NOAC (active substance, start/stop date, dose and dose changes, reason for switch to new NOAC): number of patients that switch their first or further NOAC and mean number of switches.
 - Total time in NOAC treatment
 - History and current antiplatelet treatment (yes/no, start date, end date, active substance).

[figure not shown]
Figure 1 OAC treatment management

3. Clinical Frailty Scale grading, CFS, ([19](#)) at the time of the study visit, by current NOAC type.

4. The first NOAC usage by NOAC type, for primary prevention or secondary prevention, at the time of first NOAC initiation.

Timeframe to complete data collection for the secondary outcomes is one day, the study visit day.

9.3.3 Covariates

The following covariates, related to the secondary outcome, will be collected from medical records or at the study visit (refer to [section 9.4](#)) to describe the patient's characteristics:

Table 3 Patient characteristics at the time of the study visit

Variable*	Obtained from medical records	Obtained at the study visit
Demographic characteristics: Age, sex, height, weight, BMI, caregiver (Yes/No), place where patient is living (Home alone; At home with partner/other family member/a friend; Other's home (e.g family member's); Nursing home)	x	x
Smoking habit (past/current/non-smoker) and alcohol consumption (casual/habitual/abuse/dependence)	x	x
Analytical lab results (from last available blood sample analysis): - Kidney function: serum creatinine (mg/dl), creatinine clearance (Cockcroft-Gault calculation) - Liver function: AST/ALT, total bilirubin - Hemoglobin and platelet levels	x	
NVAF: - Diagnosis date (month and year) - Type (persistent, long standing persistent, permanent, paroxysmal) - Modified EHRA scale for AF related symptoms (23) (Refer to Annex 3).	x	x (mEHRA scale)
Procedures and interventions: - Cardioversion/Ablation (Yes/No) - Coronary interventions (Yes/No): Percutaneous coronary intervention (PCI)/Coronary Artery Bypass Grafting (CABG) - Pacemaker carrier (Yes/No)	x	
History of thromboembolic events (Yes/No, number): TIA, ischemic stroke, hemorrhagic stroke, embolism systemic, deep vein thrombosis, pulmonary embolism, stable angina, unstable angina, myocardial infarction with/without ST segment elevation; and bleeding events (Yes/No): intracranial, digestive, genitourinary, gingival, nasal, pulmonary, articular-muscular, conjunctival.	x	
Other concomitant treatments (Total number of current concomitant drugs; Type (Yes/No, number): ARB or ACE inhibitor, Beta-blocker, Calcium channel blockers, Diuretics, Amiodarone, Statin, Proton pump inhibitor, H2-	x	

Variable*	Obtained from medical records	Obtained at the study visit
receptor antagonist, , Digoxin, NSAIDs, Verapamil / Dronedaron, Other antiarrhythmics, ketoconazole systemic), ciclosporine, itraconazol)		
Comorbidities and Clinical Risk Factors: - Heart Failure (Yes/No, New York Heart Association (NYHA) classification (24) (Refer to Annex 3); Left Ventricular Ejection Fraction, LVEF, %) - Coronary artery disease (Yes/No) - Sleep apnoea-hypopnoea syndrome (SAHS) (Yes/No) - Hypertension (Yes/No) - Comorbidity Charlson index (25) (Refer to Annex 3) (Yes/No; total score): myocardial infarction (already collected for history of thromboembolic events), congestive heart failure (already collected for the NHYA scale scoring), cerebral and peripheral vascular disease, dementia, chronic obstructive pulmonary disease, connective tissue disease, peptic ulcer disease, mild/moderate/severe liver disease, diabetes, diabetes with end-organ damage, hemiplegia, moderate/severe renal disease, any solid tumor, metastatic solid tumor, leukemia, lymphoma AIDs, age (already collected as a demographic characteristic).	x	x (NYHA classification, Charlson Index)
CHA2DS2-VAS (total score)		x
HAS-BLED(total score)		x

* Refer to [section 9.4](#) for more details about how these variables will be collected.

